### **5.7.2** Additional Shipping Information

### Shipping of FFPE Blocks and Glass Slides Using Supplies Provided by the Institution

- 1. Before packaging blocks or slides, verify that each specimen is labeled according to Section 5.4.2.
- 2. Blocks should be placed in a hard-sided container, preferably a special block holder, to protect the specimen. Glass slides are to be placed in plastic slide holders. Place tissue paper on top of the separated slides prior to closing the slide holder to reduce slide movement during shipment.
- 3. Place the blocks or slides in a reinforced cardboard shipping box with appropriate packaging filler to minimize movement of specimens within the shipping box.
- 4. Include a copy of the forms listed above and a shipping manifest from the Specimen Tracking System with each shipment.
- 5. Please include a cold pack when shipping on hot days and extra insulation on cold days.
- 6. Ship specimens to the address listed below. FedEx Priority Overnight is strongly recommended to prevent delays in package receipt.

# Shipping Blood or Bone Marrow Using Supplies Provided by the Institution

- 1. Before packaging specimens, verify that each specimen is labeled according to the instructions in 5.4.2.
- 2. Place the collection tubes into zip-lock bags.
- 3. Next, place specimens into a biohazard envelope with absorbent material. Expel as much air as possible and seal the envelope securely.
- 4. Place the biohazard envelope into a Tyvek envelope. Expel as much air as possible and seal securely.
- 5. Place packaged collection tube(s) and a copy of the shipping manifest from the Sample Tracking System into a sturdy shipping container. In winter months, please use an insulated container and include extra insulation (such as bubble wrap) inside the shipping container to prevent specimens from freezing.
- 6. Close the container and tape shut.
- 7. Attach a shipping label to the top of the shipping container.
- 8. Attach an Exempt Human Specimen sticker to the side of the container.
- 9. Ship specimens via overnight courier to the address below. FedEx Priority Overnight is strongly recommended to prevent delays in package receipt.

## **Shipping Frozen Serum Using Supplies Provided by the Institution**

- 1. Before packaging specimens, verify that each specimen is labeled according to the instructions in 5.4.2 and the lids of all primary receptables containing liquid are tightly sealed.
- 2. Place the specimens in zip-lock bags. Use a separate zip-lock bag for each specimen type and time point.
- 3. Place the zip-lock bags in a biohazard envelope containing absorbent material. Expel as much air as possible and seal securely.
- 4. Put the secondary envelope into a Tyvek envelope. Expel as much air as possible and seal securely.
- 5. Place frozen specimens in the insulated shipping container with dry ice. Layer the bottom of the compartment with dry ice until it is approximately one-third full. Place the frozen specimens on top of the dry ice. Cover the specimens with the dry ice until the shipping container is almost completely full. When packaging specimens, ensure that you leave enough room to include at least 5 pounds of dry ice in the shipment.
- 6. Insert a copy of the required forms into a plastic bag and place in the shipping container.
- 7. Close the lid of the shipping container and tape it shut with durable sealing tape. Do not completely seal the

container.

- 8. Complete a FedEx air bill and attach to top of shipping container.
- 9. Complete a dry ice label.
- 10. Attach the dry ice label and an Exempt Human Specimen sticker to the side of the shipping container.
- 11. Ship specimens via overnight courier to the address below. FedEx Priority Overnight is strongly recommended to prevent delays in package receipt.

# Shipping Frozen Tissue in a Single-Chamber Kit

- 1. Before packaging specimens, verify that each specimen is labeled according to the instructions in 5.4.2.
- 2. Place the specimens in zip-lock bags. Use a separate zip-lock bag for each specimen type and time point.
- 3. Place the zip-lock bags in the biohazard envelope containing absorbent material. Expel as much air as possible and seal securely.
- 4. Put the secondary envelope into a Tyvek envelope. Expel as much air as possible and seal securely.
- 5. Place frozen specimens in the kit compartment with dry ice. Layer the bottom of the compartment with dry ice until it is approximately one-third full. Place the frozen specimens on top of the dry ice. Cover the specimens with the dry ice until the compartment is almost completely full. When packaging specimens, ensure that you leave enough room to include at least 5 pounds of dry ice in the shipment.
- 6. Insert a copy of the required forms into a plastic bag and place in the kit chamber.
- 7. Place the Styrofoam lid on top to secure specimens during shipment. Do not tape the inner chamber shut.
- 8. Close the outer lid of the Specimen Procurement Kit and tape it shut with durable sealing tape. Do not completely seal the container.
- 9. Complete a FedEx air bill and attach to top of shipping container.
- 10. Complete a dry ice label.
- 11. Attach the dry ice label and an Exempt Human Specimen sticker to the side of the shipping container.
- 12. Ship specimens via overnight courier to the address below. FedEx Priority Overnight is strongly recommended to prevent delays in package receipt.

#### **5.7.3** Required Forms for Specimen Submissions

Sample label data should be entered into the specimen transmittal forms in RAVE for tumor tissue and bone marrow samples. Sample label data for blood should be recorded on the sample worksheets, which must accompany the sample shipments and be uploaded to RAVE. See below for required forms.

	Required Forms			
Tissue	1.Specimen transmittal forms in RAVE 2.Corresponding Pathology Report			
Bone Marrow Aspirate	1.Specimen transmittal forms in RAVE 2.Corresponding Bone Marrow Report (once available)			
Blood or Serum	See the following appendices: Appendix G: Pharmacokinetic Worksheet for Magrolimab, Arm A Appendix H: Pharmacokinetic Worksheet for Magrolimab, Arm B Appendix I: Anti-Drug Antibody (ADA) Worksheet for Magrolimab, Arm B			

Magrolimab

Appendix J: FcR Receptor for Polymorphism Worksheet for Arm

A

Appendix K: FcR Receptor for Polymorphism Worksheet for

Arm B

Appendix L: KiR Phenotyping Worksheet for Arm A

Appendix M: KiR Phenotyping Worksheet for Arm B

Appendix N: Human Anti-Chimera Antibodies (HACA) Testing Worksheet Arm A

Appendix O: Human Anti-Chimera Antibodies (HACA) Testing Worksheet Arm B

Appendix P: Luminex for Peripheral Cytokines Worksheet for Arm A

Appendix Q: Luminex for Peripheral Cytokines Worksheet for Arm B

Appendix R: CyTOF for Peripheral Immune Subsets Worksheet

for Arm A Appendix S: CyTOF for Peripheral Immune Subsets Worksheet

for Arm B

#### 6 TREATMENT AND IMAGING PLAN

This is a phase 1 trial dose finding trial with Hu5F9-G4 (magrolimab) a recombinant humanized IgG4 monoclonal antibody, given in combination with dinutuximab (Unituxin®), a GD2-binding monoclonal antibody for children and young adults with relapsed/refractory (R/R) NB and relapsed osteosarcoma. The first cohort of patients will receive a Safety Lead-In of single agent Hu5F9-G4 (magrolimab) at Dose Level 1 (30 mg/kg) followed by Hu5F9-G4 (magrolimab) in combination with dinutuximab as described in Section 6.1.1. Once the safe dose of the combination is established, patients will be enrolled to one of four expansion cohorts who receive the combination of Hu5F9-G4 (magrolimab) at the recommended phase 2 dose (RP2D) and a fixed dose of dinutuximab as outlined in Section 6.4.

Treatment will be administered on both an inpatient and outpatient basis. Dinutuximab is administered inpatient, while Hu5F9-G4 (magrolimab) can be given on an outpatient basis.

Reported adverse events and potential risks are described in **Section 10**. Appropriate dose modifications are described in **Section 7**.

No investigational or commercial agents or therapies other than those described below may be administered with the intent to treat the patient's malignancy.

The Study Calendars in Section 11 outline the timing of procedures and visits.

### 6.1 Agent Dose and Administration

All patients, regardless of whether they are enrolled on the "single agent Safety Lead-In" Dose Finding Cohort (Arm A) or the Expansion Cohorts (Arm B), will receive a priming dose of Hu5F9-G4 (magrolimab) (1 mg/kg) intravenous (IV) on Day 1 of week 1 (see Figure 1 and Figure 2).

# **6.1.1** Dose Finding Cohort (Arm A)

There will be two evaluations for dose limiting toxicity (DLT) conducted on this study in Arm A (see **Figure 1** and **Figure 2**).

### 6.1.1.1 Safety Assessment During "single agent Safety Lead-In"

Patients aged ≥2 or < 18 years of age will be enrolled on the "single agent Safety Lead-In", and will receive a therapeutic dose of Hu5F9-G4 (magrolimab) (30 mg/kg IV) on Day 1 of weeks 2 and 3 for a 21-day "single agent Safety Lead-In" cycle (see **Figure 1** and **Figure 2**). An assessment for DLTs as defined in **Section 6.3** will be performed during and at the end of the 21-day "single agent Safety Lead-In".

Any patient who does not develop DLT during the "single agent Safety Lead-In" may proceed to Cycle 1 (combination therapy with Hu5F9-G4 (magrolimab) plus dinutuximab) and will be evaluable for safety assessment during and after Cycle 1. When dinutuximab is administered immediately after Hu5F9-G4 (magrolimab), redosing with acetaminophen and diphenhydramine is not necessary. The intravenous line should be flushed well between drug administrations.

Patient enrollment and start of treatment during the safety "single agent Safety Lead-In" assessment will be staggered by 7 days for each patient enrolled. Three patients will initially be enrolled at Dose Level 1 (30 mg/kg IV).

- If 0 of the initial 3 patients develops a DLT during the 21-day "single agent Safety Lead-In", the next phase of safety will be evaluated in Cycle 1 as outlined below (Section 6.1.1.2).
- If 1 of the initial 3 patients develops a DLT (Section 6.3) during the 21-day "single agent Safety Lead-In", then an additional 3 patients will be enrolled at Dose Level 1.
  - o If 0 of these 3 additional patients (totaling 1/6) develops a DLT during the 21-day "single agent Safety Lead-In", the study will continue to evaluate DLTs in Cycle 1 as outlined below (Section 6.1.1.2).
  - o If ≥1 of these 3 additional patients (totaling 2/6) develop a DLT, the dose of Hu5F9-G4 (magrolimab) will be de-escalated to Dose Level -1 (20 mg/kg) during weeks 2 and 3 in the next 3 patients. The safety of Dose Level -1 will be similarly evaluated in 3-6 patients.
- If ≥ 2 of the initial 3 patients develop a DLT during the 21-day "single agent Safety Lead-In", the dose of Hu5F9-G4 (magrolimab) will be de-escalated to Dose Level -1 (20 mg/kg) during weeks 2 and 3, in the next 3 patients. The safety of Dose Level -1 will be similarly evaluated in 3-6 patients.
- If ≥ 2 patients develop DLT during the "single agent Safety Lead-In" using Dose Level -1, enrollment will pause pending discussions with the sponsor, IRB and FDA.

Any patient who develops a DLT during the "single agent Safety Lead-In" will be removed from additional therapy on this study.

#### 6.1.1.2 Safety Assessment During Cycle 1

An assessment for DLTs will be performed during and at the end of the 21 days of Cycle 1 (Figure 2). In the absence of

DLTs or progressive disease (PD), patients may proceed to a maximum of 12 cycles of combination therapy. After Cycle 2, each subsequent cycle will consist of Hu5F9-G4 (magrolimab) administered on Day 1 of weeks 1 and 3 of the cycle (week 2 will be a week of rest), with dinutuximab administration on Day 2 through 5 of week 1.

The initial dosing of each patient during Cycle 1 safety assessment will be staggered by 7 days for each patient. Three weeks (21 days) must elapse after completion of Cycle 1 in the final patient in the dose finding cohort (Arm A) to allow for safety assessment before treating additional patients at the determined recommended phase 2 dose (RP2D) in Arm B.

The following rules apply to the DLT assessment conducted at the conclusion of Cycle 1 (week 6).

If Dose Level 1 is selected as safe for Cycle 1 based on safety results from the 'Single agent Safety Lead-In', three patients will be enrolled, and the following applies:

- If 0 of the initial 3 patients develops a DLT during Cycle 1, the study will proceed to the expansion cohorts (Arm B) (see Section 6.4).
- If 1 of the initial 3 patients develops a DLT during Cycle 1, then an additional 3 patients will be enrolled at Dose Level 1
  - o If 0 of these 3 additional patients (totaling 1/6) develops a DLT during Cycle 1, the study will proceed to the expansion cohorts (Arm B) (see Section 6.4).
  - If ≥ 1 of these 3 additional patients (totaling ≥ 2/6) develop a DLT during Cycle 1, an additional 3 patients will be enrolled to receive the priming dose followed by Hu5F9-G4 (magrolimab) de-escalated to Dose Level -1 (20 mg/kg) during Cycle 1 (Table 4). The safety of Dose Level -1 will be similarly evaluated in 3-6 patients.
  - If 2 of the initial 3 patients develop a DLT during Cycle 1, an additional 3 patients will be enrolled to receive the priming dose followed by Hu5F9-G4 (magrolimab) de-escalated to Dose Level -1 (20 mg/kg) during Cycle 1. The safety of Dose Level -1 will be similarly evaluated in 3-6 patients.

Table 4: Doses for Hu5F9-G4 (magrolimab) and Dinutuximab during Dose Finding Cohort (Cycle 1)

Dose Level	Dose of (magrolimab)	Hu5F9-G4	Dose of Dinutuximab
Level -1	20 mg/kg IV		17.5 mg/m  IV
Level 1	30 mg/kg IV		17.5 mg/m  IV

The dose level of Hu5F9-G4 (magrolimab) that is deemed safe during both the 'Single agent Safety Lead-In' and Cycle 1 in the dose finding cohort (Arm A) will be used to evaluate safety in the Arm B schedule. The first three (3) patients enrolled to Arm B will be evaluated for DLT, and three weeks (21 days) must elapse after completion of Cycle 1 in the final patient to allow for safety assessment before treating additional patients in Arm B to confirm the recommended phase 2 dose (RP2D) (Arm B) (see Section 6.2.1.2). These three patients will be allocated and analyzed in their respective cohorts for efficacy analysis.

If protocol therapy is delayed (due to re-scheduling for administrative reasons or temporary suspension due to toxicity), disease evaluations and correlative exploratory biology studies will follow the originally scheduled calendar dates and should *not* be adjusted for the dose delay. The results of these evaluations and assays while on treatment should reflect the effect of the former dose(s), not the current/prospective clinical status at the time of drug administration. All clinical assessments and laboratory tests (and their respective windows) will adjust with the dose delay to reflect the patient's clinical

status at the time of drug administration.

The Study Calendars in Section 11 outline the timing of procedures and visits for Arm A and Arm B.

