#### **Trial Schema ARMS ARM B: Four Expansion Cohorts** ARM A: Single Agent Safety Lead-In & Cycle 1 **B1.** Measurable NBL **DOSE LEVEL 1 B2. Evaluable NBL 0-1 DLTs** 30 mg/kg magrolimab RP2D magrolimab **B3.** Measurable + 17.5mg/m^2 $+ 17.5 \text{mg/m}^2$ Osteosarcoma dinutuximab with **B4.** Osteosarcoma dinutuximab safety lead-in w/resectable (6 patients) pulmonary only relapse DOSE LEVEL -1 0-1 ≥ 2 **DLTs DLTs STOP TRIAL** ≥ 2 DLTs

[figure not shown]

Figure 2: Trial Schedule Schema

If ≥2 DLTs at Dose Level 1 (after week 3 or week 6), then reduce to DL-1 (20 mg/kg) and assess for safety, If ≥ 2 DLTs at DL-1, then STOP study

A. After cycle 2, Hu5F9-G4 (magrolimab) will be administered on Day 1 of the 1st and 3rd week of every subsequent cycle. Cycles may be repeated in the absence of disease progression or toxicity to a maximum of 12 cycles.

A. After cycle 2, Hu5F9-G4 (magrolimab) will be administered on Day 1 of the 1st and 3rd week of every subsequent cycle. Cycles may be repeated in the absence of disease progression or toxicity to a maximum of 12 cycles.

B1: Measurable NB B2: evaluable NB

B3: measurable OS

B4: OS with resectable pulmonary only relapse

pulmonary metastasectomy after at least 1 cycle and will require delay in starting subsequent cycle (for a maximum of 5 cycles post resection)

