# 6.2 Regimen Description and Supportive Care Guidelines

- **6.2.1** Hu5F9-G4 (Magrolimab) and Dinutuximab (Unituxin®) Agent Administration
- 6.2.1.1 Dose Finding Cohort (Arm A) Regimen

Table 5: Regimen Description for Dose Finding Cohort (Arm A)

Agent	Premedications; Precautions	Dose	Route	Schedule	Cycle Length
Hu5F9-G4 (magrolimab)	Administer according to guidelines in Section 6.2.1.3. Acetaminophen oral (PO) and diphenhydramine (IV) or a comparable regimen up to 15 minutes before the first two doses of Hu5F9-G4 (magrolimab), and in case of re-priming of the patient after > 4 weeks interruption in treatment. Monitor for infusion reactions during and	mg) of acetaminophen; 0.5 - 1 mg/ kg (max 50 mg) of diphenhydramine^  Priming: Hu5F9-G4 (magrolimab) - 1 mg/kg  "Single Agent Safety Lead-In": Hu5F9-G4 (magrolimab) 30 mg/kg*  Cycles 1 and subsequent cycles: Hu5F9-G4 (magrolimab) 30	PO; Diphenhydramin e IV  Priming: Infuse IV (peripheral or central line) over 3 hours (± 30 min)  Subsequent infusions: Infuse IV over 2 hours	-	21 days (3 weeks)
Dinutuximab	Administration requires premedication	10 mg/kg (max 650 mg) of		Cycles 1 (Week 1): Days 2-5;	

(acetaminophen -	- 1 mg/ kg (max 50	e^ IV (no need to	Cycle 2 (Week
oral,	0 0 1	be repeated if	` `
diphenhydramine -	O ,	dinutuximab	-,- = -,-
IV, and analgesia)			Subsequent
and hydration prior to		follows previous	
initiation according to		drug infusion)	
Section 6.2.1.4	Dinutuximab - 17.5		week of each
	$mg/m^2$	Analgesia as	subsequent
		described below	cycle
		in Section	
		6.2.1.4 .	
		Dinutuximab in	
		100 mL bag of	
Administer 0.9%		0.9% Sodium	
Sodium Chloride		Chloride	
Injection USP 10		Injection USP	
mL/kg as an IV over 1		(mix by gentle	
hour prior to initiating		inversion - DO	
drug infusion		NOT shake)	

\* Dose will be de-escalated to 20 mg/kg if 2 or more patients develop DLT during the "Single Agent Safety Lead-In" or Cycle 1.

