#### **9.3.3** Sample Size Justification

A minimum of 4 patients will be enrolled on this trial if two patients at Dose Level 1 have DLTs and 2 patients at Dose Level -1 have DLTs.

A maximum of 82 patients will be enrolled on this trial:

- Six patients/dose level at Dose Level 1 and Dose Level -1 = 12
- Three expansion cohorts (B1, B2 and B3) of 20 patients in each cohort
- Ten patients in cohort B4.

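### One lead-in DLT plus one Cycle 1 DLT at Dose Level 1 gives 30 mg/kg under 6.1.1 but 20 mg/kg under the Table 5 footnote read literally; the per-period reading does not fit six per level

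*Combined protocol and SAP*

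**What the plan says.** Section 6.1.1.1 runs a 3+3 count on the lead-in. At one DLT in six, "the study will continue to evaluate DLTs in Cycle 1 as outlined below". A child with a lead-in DLT "will be removed from additional therapy on this study".

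Section 6.1.1.2 then runs a second 3+3 count, confined to Cycle 1. It passes Dose Level 1 at 0/3, or at one in six: "totaling 1/6) develops a DLT during Cycle 1, the study will proceed to the expansion cohorts (Arm B". It closes by saying that the level found safe in both periods "in the dose finding cohort (Arm A) will be used to evaluate safety in the Arm B schedule". Neither section adds DLTs across the two periods.

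The footnote to Table 5 (Section 6.2.1.1) reads "Dose will be de-escalated to 20 mg/kg if 2 or more patients develop DLT during the" lead-in or Cycle 1. The note in the schema says "If ≥2 DLTs at Dose Level 1 (after week 3 or week 6), then reduce to DL-1 (20 mg/kg"), and the Figure 1 text labels the block "ARM A: Single Agent Safety Lead-In & Cycle 1".

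Section 9.3.3 builds the maximum of 82 on "Six patients/dose level at Dose Level 1 and Dose Level -1 = 12". Section 9.2.1 replaces patients who leave for reasons other than a DLT, and does so within the group concerned (lead-in or Cycle 1).

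**The concern.** The recommended phase 2 dose is a primary objective (1.1.2). For one foreseeable result, the document gives two answers. Two children at Dose Level 1 have a DLT, one in each period. They must be different children, because the first leaves treatment. Section 6.1.1 passes the level; the footnote, taken at its word, reduces it. The weekly review described in 13.1.2 would see both events, but nothing states which count governs. The choice would then be made with the data in hand, when the dose for the next children depends on it.

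**Working it through.** **1. The plan's own totals.** Section 9.3.3: 2×6 + 3×20 + 10 = 12 + 60 + 10 = 82, as stated. The minimum is 2 + 2 = 4, which fits either way of counting.

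**2. The path in dispute.** Lead-in: 1/3, then 0/3, giving 1/6; continue. One child is removed, so five remain. Cycle 1: 1/3, then 0/3, giving 1/6; pass. Section 6.1.1 gives 30 mg/kg. The footnote's condition (two patients with DLT during the lead-in or Cycle 1) is met, which gives 20 mg/kg.

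**3. Enrolment under separate counts.** Children who finish the lead-in without DLT are evaluable in Cycle 1 (6.1.1.1), so they are reused here.

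- Dose Level 1: 6 − 1 = 5 remain and Cycle 1 needs six, so one more child is enrolled: 7. That child is not a replacement under 9.2.1, because the vacancy arose from a DLT.
- If Dose Level 1 then fails in Cycle 1, 6.1.1.2 starts Dose Level -1 with the priming dose and Cycle 1, with no lead-in. That level needs at most 6: 7 + 6 = 13.
- Dose Level -1 can reach 7 only if Dose Level 1 failed in the lead-in, which uses at most 6: 6 + 7 = 13.
- Overall: 13 + 60 + 10 = 83.

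Under a pooled count the second DLT ends the level, so it never needs more than 6, and 12 and 82 stand.

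**4. How often the rules disagree.** The documents give no DLT rate for children. Assume an overall risk *r* per child, split equally, so the risk per period is p = 1 − √(1 − r), and q = 1 − p. Children added in Cycle 1 after a clean lead-in are taken to go straight to Cycle 1, as 9.2.1 allows for replacements once the lead-in has been found safe.

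- One period passes at 0/3 with probability q³, and at 1/6 with probability 3pq²·q³ = 3pq⁵.
- Pass under separate counts: S = (q³ + 3pq⁵)².
- Disagreement, lower value (1/6 in each period): (3pq⁵)².
- Disagreement, upper value: add 3pq⁵·q³·(1 − q²). This is a 1/6 lead-in, 0/3 in the first three Cycle 1 children, then a DLT in one or both of the other two. It applies if all five remaining children are treated in Cycle 1.
- Pass under pooled counts: S minus the disagreement.

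For r = 0.20: p = 1 − √0.8 = 0.1056, q³ = 0.7155 and 3pq⁵ = 0.1813. Then S = 0.8968² = 0.804. The lower value is 0.1813² = 0.0329. The upper value is 0.0329 + 0.1813×0.7155×0.20 = 0.0588.

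| Overall risk | p per period | 30 mg/kg passes, separate | Rules disagree | 30 mg/kg passes, pooled | Disagree, given lead-in 1/6 |
|---|---|---|---|---|---|
| 10% | 0.0513 | 0.945 | 0.014–0.024 | 0.921–0.931 | 0.12–0.20 |
| 20% | 0.1056 | 0.804 | 0.033–0.059 | 0.746–0.771 | 0.18–0.32 |
| 33% | 0.1835 | 0.554 | 0.040–0.076 | 0.478–0.514 | 0.20–0.38 |
| 40% | 0.2254 | 0.427 | 0.036–0.071 | 0.356–0.391 | 0.19–0.37 |

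The last column divides the disagreement by 3pq⁵, the probability of a 1/6 lead-in.

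**The case against.** The best defence is that the operative text is consistent and counts separately. Section 6.1.1 announces two DLT evaluations. Sections 6.1.1.1 and 6.1.1.2 each give a complete algorithm for one period, and the dose must be found safe in both. Section 9.2.1 speaks of two timepoints and lets some replacements skip the lead-in, which implies separate denominators. On this view the footnote's *or*, and the schema's week 3 or week 6, simply name the two checkpoints. The figure could not be read in full, so its Arm A label is weak evidence for pooling. All of this stands as a fair reading. It does not remove the problem: no page says the footnote is per period, and separate counts then exceed the six per level in 9.3.3.

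A reader might go further and infer that six per level proves pooling was intended. The documents do not support that. The excess is one patient on particular branches, and 82 already leaves out the replacements that 9.2.1 allows. Nor does seven at each level, giving 14 and 84, follow: the two dose levels cannot both reach seven on one path.

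The defence is also right that exposure is checked early. The first three Arm B patients are assessed for DLT, with a 21-day wait, before others are treated (6.1.1.2), and 6.4 adds a trigger at two of the first five or at least two of six. In adults with solid tumours or lymphoma, 30 mg/kg is already the recommended dose, with no maximum tolerated dose reached (2.1.6). These checks limit harm but do not say which count governs. The three-patient check states no DLT number that lowers the dose, and the 6.4 trigger leads to a discussion.

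**Conclusion.** The point holds as a conflict in a stated dose rule. After one DLT in each period at Dose Level 1, 6.1.1 selects 30 mg/kg, and the Table 5 footnote read literally selects 20 mg/kg. If the footnote and schema are meant per period, the enrolment maximum is understated by one at each step: 7 against 6 at one level, 13 against 12 in Arm A, and 83 against 82 overall. Either reading needs an edit.

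The size is modest: a disagreement probability of about 0.01 to 0.08, resting on assumed overall risks of 10% to 40% and an equal split. The larger figures, 0.12 to 0.38, apply only once the lead-in has passed at exactly 1/6. The enrolment figures assume that lead-in survivors are reused in Cycle 1, and they exclude replacements.

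A reader might infer that all 70 possible Arm B patients (3×20 + 10) would be treated at a disputed dose. The documents do not support that, because the dose goes first to three patients for confirmation. The point is still worth fixing: it affects a paediatric dose decision under a primary objective, and the remedy is a wording change.

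**What to change.** Adopt one of two rules before the situation arises.

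**(a) Separate counts.** Reword the Table 5 footnote and the schema note to: *2 or more patients in the Safety Lead-In, or 2 or more patients in Cycle 1*. Change 9.3.1 and 9.3.3 to a maximum of 13 in Arm A and 83 overall, before replacements. Cost: wording changes and one more patient in the stated maximum. This keeps 6.1.1 and 9.2.1 as they are.

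**(b) Pooled counts.** State in 6.1.1.2 that DLTs at a dose level are counted across the Safety Lead-In and Cycle 1. Amend the Cycle 1 pass bullets themselves, so that a level with one lead-in DLT passes only with no Cycle 1 DLT; an added sentence alone would contradict them. Say whether all five remaining children must complete Cycle 1. Where Dose Level -1 starts in Cycle 1 after a Cycle 1 failure, count Cycle 1 only, because there is no lead-in to pool. Cost: no added patients, with 12 and 82 unchanged, but 30 mg/kg is selected slightly less often, by 0.01 to 0.08 in absolute terms at the assumed risks.
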